13.4 Laboratory safety variables

In CRS-1 and CRS-2 no laboratory data was collected.

For LEROS data, the clinical out of normal range laboratory variables with clinically significant values will be tabulated as described in Table 13-6. Clinical significance of the out of normal range laboratory variables will be as assessed by the investigator.

Table 13-6- Increased laboratory values

	Clinically Significant	Patients	Rate	Days in Ti	reatment ¹
	Events			mean (SD)	min – max
Alanine Aminotransferase (ALT)	xx (xx.x%)	xx (xx.x%)	xx.x	xx.x (xx.x)	xx.x – xx.x
Albumin	xx (xx.x%)	xx (xx.x%)	xx.x	xx.x (xx.x)	xx.x – xx.x

Alkaline Phosphatase (ALP)	xx (xx.x%)	xx (xx.x%)	xx.x	xx.x (xx.x)	xx.x - xx.x
Aspartate Aminotransferase (AST)	xx (xx.x%)	xx (xx.x%)	xx.x	xx.x (xx.x)	xx.x – xx.x
Bicarbonate	xx (xx.x%)	xx (xx.x%)	xx.x	xx.x (xx.x)	xx.x – xx.x
Calcium	xx (xx.x%)	xx (xx.x%)	xx.x	xx.x (xx.x)	xx.x – xx.x
Chloride	xx (xx.x%)	xx (xx.x%)	xx.x	xx.x (xx.x)	xx.x - xx.x
Cholesterol	xx (xx.x%)	xx (xx.x%)	xx.x	xx.x (xx.x)	xx.x – xx.x
Creatine	xx (xx.x%)	xx (xx.x%)	xx.x	xx.x (xx.x)	xx.x – xx.x
Gamma GT (GGT)	xx (xx.x%)	xx (xx.x%)	xx.x	xx.x (xx.x)	xx.x – xx.x
Glucose	xx (xx.x%)	xx (xx.x%)	xx.x	xx.x (xx.x)	xx.x – xx.x
Inorganic Phosphate	xx (xx.x%)	xx (xx.x%)	xx.x	xx.x (xx.x)	xx.x – xx.x
Potassium	xx (xx.x%)	xx (xx.x%)	xx.x	xx.x (xx.x)	xx.x – xx.x
Sodium	xx (xx.x%)	xx (xx.x%)	xx.x	xx.x (xx.x)	xx.x – xx.x
Total Bilirubin	xx (xx.x%)	xx (xx.x%)	XX.X	xx.x (xx.x)	xx.x - xx.x
Total Protein	xx (xx.x%)	xx (xx.x%)	xx.x	xx.x (xx.x)	xx.x – xx.x
Triglycerides	xx (xx.x%)	xx (xx.x%)	XX.X	xx.x (xx.x)	xx.x – xx.x
Urea or BUN	xx (xx.x%)	xx (xx.x%)	xx.x	xx.x (xx.x)	xx.x – xx.x
Uric Acid	xx (xx.x%)	xx (xx.x%)	xx.x	xx.x (xx.x)	xx.x – xx.x
Basophils	xx (xx.x%)	xx (xx.x%)	xx.x	xx.x (xx.x)	xx.x – xx.x
Eosinophils	xx (xx.x%)	xx (xx.x%)	xx.x	xx.x (xx.x)	xx.x – xx.x
HGB	xx (xx.x%)	xx (xx.x%)	xx.x	xx.x (xx.x)	xx.x - xx.x
Haematocrit	xx (xx.x%)	xx (xx.x%)	xx.x	xx.x (xx.x)	xx.x - xx.x
Lymphocytes	xx (xx.x%)	xx (xx.x%)	XX.X	xx.x (xx.x)	xx.x – xx.x
MCH	xx (xx.x%)	xx (xx.x%)	xx.x	xx.x (xx.x)	xx.x – xx.x
MCHC	xx (xx.x%)	xx (xx.x%)	xx.x	xx.x (xx.x)	xx.x – xx.x

MCV	xx (xx.x%)	xx (xx.x%)	xx.x	xx.x (xx.x)	xx.x – xx.x
Monocytes	xx (xx.x%)	xx (xx.x%)	xx.x	xx.x (xx.x)	xx.x – xx.x
Neutrophils	xx (xx.x%)	xx (xx.x%)	xx.x	xx.x (xx.x)	xx.x – xx.x
Platelet Count	xx (xx.x%)	xx (xx.x%)	xx.x	xx.x (xx.x)	xx.x – xx.x
RBC Count	xx (xx.x%)	xx (xx.x%)	xx.x	xx.x (xx.x)	xx.x – xx.x
WBC Count	xx (xx.x%)	xx (xx.x%)	xx.x	xx.x (xx.x)	xx.x – xx.x
Urine Blood	xx (xx.x%)	xx (xx.x%)	xx.x	xx.x (xx.x)	xx.x – xx.x
Urine Glucose	xx (xx.x%)	xx (xx.x%)	xx.x	xx.x (xx.x)	xx.x – xx.x
Urine Ketones	xx (xx.x%)	xx (xx.x%)	xx.x	xx.x (xx.x)	xx.x - xx.x
Urine Protein	xx (xx.x%)	xx (xx.x%)	xx.x	xx.x (xx.x)	xx.x – xx.x
Urine pH	xx (xx.x%)	xx (xx.x%)	xx.x	xx.x (xx.x)	xx.x - xx.x

¹ Days since start of treatment at the time of event;

Listings: It will be provided a listing with date of visit, visit type (baseline, follow-up month or unscheduled), lab test name, lab test value, lab test unit, order by center, patient identification and date of visit.

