idebenone therapy and CRR, where possible compared to untreated control patients.

The treatment duration in RHODOS was 6 months and a larger proportion of idebenone-treated patients presented with CRR in VA compared to placebo. However, data from Santhera's ongoing Expanded Access Program (EAP) indicates that prolonged treatment can increase both the proportions of patients with CRR of VA and the magnitude of the recovery observed. Furthermore, data from the RHODOS and from the EAP provide evidence that the LHON-causative mutation harboured is prognostic of CRR in VA. Therefore, secondary objectives of this study are to provide information on the effect of treatment duration on both the proportions of patients presenting with CRR and on the magnitude of any response with increasing treatment time and on the influence of the mutation harboured on CRR rate compared to spontaneous CRR (sCRR) in untreated control patients.

The study will also allow the assessment of the safety and tolerability of long-term treatment with idebenone, with particular emphasis on the proportion of patients experiencing elevated Liver Function Tests (LFTs) or changes in blood cell counts.

Number of Centres

Approximately 35

Multinational study with US sites operating under IND and EU sites not operating under IND.

Number of Patients

80 patients presenting ≤1 year after the onset of symptoms will be enrolled to ensure 61 provide VA assessments following 12 months of idebenone treatment (primary endpoint).

80 patients presenting >1 year after the onset of symptoms will be enrolled to ensure 61 provide VA assessments following 12 months of idebenone treatment (secondary endpoint). Patients will be stratified according to time since onset of symptoms with a maximum of 30 patients to be enrolled in any of the strata of >1 - \leq 2 years, >2 - \leq 3 years, >3 - \leq 4 years and >4 - \leq 5 years since onset of symptoms.

Inclusion Criteria

- 1. Impaired visual acuity in affected eyes due to LHON
- 2. No explanation for visual loss besides LHON
- 3. Age \geq 12 years
- 4. Onset of symptoms ≤5 years prior to Baseline
- 5. Confirmation of either G11778A, G3460A or T14484C LHON mtDNA (for the ITT population, not required for enrolment)
- 6. Written informed consent obtained from the patient
- 7. Ability and willingness to comply with study procedures and visits

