Proportions of Patients and Eyes in the EAP with CRR from VA Nadir following 6 months and 12 months of treatment

CRR from Nadir	Patients		Eyes		Treatment duration at assessment [months]			
in the Efficacy Population	all	CRR	all	CRR	mean	(SD)	min	max
Patients with 6m assessment available	62	CRR at 6m 19 (30.6%)	124	CRR at 6m 30 (24.2%)	5.8	(1.0)	3.1	8.1
12m assessment available	47	CRR at 12m 17 (36.2%)	94	CRR at 12m 28 (29.8%)	11.6	(1.3)	9.1	13.9
at last observation	69	CRR at last obs. 34 (49.3%)	138	CRR at last obs. 55 (39.9%)	15.4	(9.0)	2.8	36.2

6m assessment : closest to 6 months, values at 3-9 months considered

12m assessment: closest to 12 months, values at 9-15months considered

Source Tables : EAP 01-01, EAP 01-02, EAP 01-03, EAP 02-01, EAP, 02-02, EAP 02-03

Magnitude of Recovery in Eyes in the EAP with CRR from VA Nadir at the 6 month, 12 month or at the last observation

Recovery* from Nadir [logMAR]**	N	mean	SD	median	max	min
at the 6 month vist	15	-0.47	0.31	-0.38	-1.00	-0.14
at the 12 month vist	15	-0.62	0.48	-0.40	-1.40	-0.10
at last observation (mean treat. dur. 20.9 m)	15	-0.93	0.42	-1.08	-1.44	-0.14

^{*}for eyes with CRR from BL where recovery had occured at the 6 months visit and a 12 month visit was available, too

Note, for these 15 eyes the VA at BL was also the VA at Nadir

Furthermore, data from the RHODOS and from the EAP provide evidence that the LHON-causative mutation harboured is prognostic of CRR in VA.

Therefore, secondary objectives of this study are to provide information on the effect of treatment duration on both the proportions of patients presenting with CRR and on the magnitude of any response with increasing treatment time and on the influence of the mutation harboured on CRR rate compared to spontaneous CRR (sCRR) untreated control patients.

The study will also allow the assessment of the safety and tolerability of long-term treatment with idebenone, with particular emphasis on the proportion of patients experiencing elevated Liver Function Tests (LFTs) or changes in blood cell counts.

^{**}off chart set to 1.70 [logMAR]

2 Study Objectives and Endpoints

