8.1.2 Adverse Events of Special Interest (AESI)

The detection, monitoring and evaluation of potential risks of idebenone are addressed in the idebenone risk management plan. AESI correspond to the important potential risks which are identified in the safety specification and listed in the Risk Management Plan and in the corresponding interface between the European Risk Management Plan and EudraVigilance. Important potential risks are important risks for which there is some basis for suspicion of a causal association with the medicinal product of interest but where this association has not been confirmed and needs further confirmed or rejected as new data on come available. Currently, there are no important identified risks, i.e. important risk for which there is adequate evidence of an association with the medicinal product of interest, listed in the idebenone RMP.

Therefore, particular attention should be paid to AESI that are described as follows as follows in this RMP and constitute important potential risks for idebenone:

- Abnormal liver function test (ALT, AST, total bilirubin, GGT) or hepatitis (liver disease)
- Blood count abnormalities (such as agranulocytosis, anaemia, leukocytopenia or thrombocytopenia)

In order to be considered as AESI, the events should in first place qualify as AE according to the guidance presented in 8.1.1 above.

Possible fluctuations of hepatic laboratory tests or blood count values which from medical history may be expected in the patient but which are not considered clinically relevant by the investigator should not be reported as AESI.

For hepatic laboratory tests listed above any change below 1.5XULN usually are considered not to be clinically relevant, but this qualification as not clinically relevant should always remain a judgment by the investigator in the individual patient.

For complete and accurate safety surveillance, the data collected on these pre-defined events will include as many details as possible to corroborate diagnosis.

AESI should be reported using the designated section of the SAE report form and transmitted to UBC with 24 hours of learning of its occurrence, regardless severity and seriousness assessment.

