9.4.3 Safety Evaluation

The disposition of the patients will be summarized by tabulating the number of enrolled, completed and discontinued patients. The reasons for premature discontinuations will be tabulated. The extent of exposure will be summarized by tabulating the duration of the study treatment.

All adverse events (AEs) will be coded using the MedDRA dictionary. The treatment-emergent AEs (i.e., events which start or worsen during the study treatment) will be tabulated by system organ class and preferred term. Both subject and event counts will be calculated. In addition, the treatment-emergent AEs will be evaluated by severity and by relationship to the study treatment. The serious AEs and AEs leading to a premature discontinuation will also be summarized.

The clinical laboratory variables and vital signs will be summarized descriptively, including a tabulation of normal and abnormal values.

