9.5 Analyses

The final analysis for the primary endpoint will be conducted at the time when all subjects enrolled in this open label intervention study have completed Visit 6/Month 12. The following efficacy and safety parameters will be reported:

Efficacy (primary endpoint):

Proportion of eyes in patients treated with idebenone ≤1 year after the onset of symptoms with CRR of VA from Baseline or in which Baseline VA better than 1.0 logMAR was maintained at Month 12, compared to matching external natural history control group

Safety (secondary endpoint):

The count of patients who experienced abnormal biochemistry, haematology and/or urine test results will be reported, compared to the Baseline assessments.

A detailed analysis plan will be prepared as part of the SAP prior to database lock.

Final analyses will be conducted and a Clinical Study Report prepared when the last patient has left the study.

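### The SAP drops the protocol's baseline-referenced summaries of abnormal laboratory results and keeps only values the investigator calls clinically significant, without declaring the change

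*SAP*

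**What the plan says.** **Protocol.** Section 9.5 lists, under safety as a secondary endpoint: "The count of patients who experienced abnormal biochemistry, haematology and/or urine test results will be reported, compared to the Baseline assessments". Section 9.4.3 states: "The clinical laboratory variables and vital signs will be summarized descriptively, including a tabulation of normal and abnormal values". Section 1.2 explains the focus, placing "particular emphasis on the proportion of patients experiencing elevated Liver Function Tests (LFTs) or changes in blood cell counts".

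**SAP.** Section 13.4 is the only laboratory analysis section. It says "the clinical out of normal range laboratory variables with clinically significant values will be tabulated as described in Table 13-6", and adds: "Clinical significance of the out of normal range laboratory variables will be as assessed by the investigator". Table 13-6 is captioned "Increased laboratory values". For each test it shows clinically significant events, patients, a rate and days in treatment. Section 13.4 also provides a listing of values by visit, baseline included. Section 13.8 closes the safety chapter by ruling out analysis of any other safety data.

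**Status of the difference.** SAP section 2 gives the SAP precedence over the protocols where they disagree. SAP section 14 says there are currently no deviations from them.

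**The concern.** The protocol's quantity is the number of patients with an abnormal result, read against baseline. The SAP's quantity is the number with an out-of-range result that an investigator also considered important, with no baseline reference. These are different counts, and because the SAP takes precedence, the narrower one would be reported.

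This matters for two reasons. First, safety has no comparator: SAP 8.1 and 13 state that the natural history surveys collected no safety data. The patient's own baseline is therefore the only reference available, and the laboratory tables do not use it. Second, the tests affected are those the protocol emphasises. The blood-count events of special interest named in protocol 8.1.2 (agranulocytosis, anaemia, leukocytopenia, thrombocytopenia) are all decreases, yet the caption of the one laboratory table speaks of increases.

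**Working it through.** Neither document gives a figure for this endpoint, so the check is mainly a comparison of text.

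**Step 1: what each document delivers.**

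| Element | Protocol 9.4.3 and 9.5 | SAP 13.4 |
|---|---|---|
| Tabulation of normal and abnormal values | Yes | No |
| Count of patients with abnormal results | Yes | Only results judged clinically significant, test by test |
| Comparison with Baseline | Yes | No baseline column, change or shift |
| Who decides that a result counts | Abnormality alone | Investigator; no numeric threshold |
| Direction | Abnormal, either way | Text: either way. Caption: increases |

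**Step 2: does another SAP output fill the gap?**

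- *Adverse events.* Under protocol 8.1.1 and 8.1.2, liver-test and blood-count abnormalities that qualify as adverse events become events of special interest. They reach the AESI row of SAP Table 13-4. However, fluctuations the investigator considers not clinically relevant are not reported by this route, so results dismissed for Table 13-6 are not recovered.
- *Listing.* The fields specified are visit date, visit type, test name, value and unit. No reference range or abnormal flag is specified. Samples are analysed in local laboratories (protocol 6.6.1 and 8.6.3), so a reader cannot derive the protocol's count from the listing.
- *Other safety sections.* SAP 13.5 gives vital signs change from baseline and shift tables. SAP 13.7 gives fundoscopy shift tables. Nothing equivalent is specified for laboratory data.

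**Step 3: direction.** The text of SAP 13.4 covers values outside the normal range on either side. Table 13-6 has rows for haemoglobin, neutrophils, platelets, red cells and white cells. Text and rows point to both directions and the caption to one. A programmer has to choose.

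**Step 4: size.** Let *a* be the share of patients with at least one out-of-range result, and *s* the share of those with at least one result judged clinically significant. The documents give neither. With N = 80 + 80 = 160 planned patients:

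- patients with an abnormal result = N × a
- patients visible in Table 13-6 = N × a × s
- share not visible = 1 − s, whatever *a* is

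For illustration, assume a = 20%, so 160 × 0.20 = 32 patients:

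| Assumed s | Visible in SAP table | Not visible |
|---|---|---|
| 10% | 32 × 0.10 = 3.2, about 3 | 90% |
| 25% | 32 × 0.25 = 8 | 75% |
| 50% | 32 × 0.50 = 16 | 50% |
| 75% | 32 × 0.75 = 24 | 25% |

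The figure of 32 is an upper limit for the protocol's count, since the protocol does not say exactly how the baseline comparison enters.

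**The case against.** The best defence has four parts. The endpoint as listed in protocol 2.2.2 (adverse event counts and laboratory analyses) is carried into SAP 4.2. Safety is descriptive, so no test is affected. A table of clinically significant values is a sensible way to separate signal from the many trivial out-of-range flags expected in healthy people. The events of special interest have their own summary, and every value is listed. All of this is fair, and it justifies keeping Table 13-6. It does not supply the two summaries the protocol promises, and precedence of the SAP settles which text governs without disclosing the change.

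Four stronger readings are tempting but not supported:

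- *Most liver-test rises and blood-count falls go uncounted.* This needs *s* below 50%, and the documents give no value for *s*.
- *Decreases are excluded.* Only the caption suggests this. The text and the blood-count rows say otherwise, so the defect is ambiguity.
- *Liver values under 1.5 times the upper limit are filtered out of Table 13-6.* The sentence that "any change below 1.5XULN usually are considered not to be clinically relevant" belongs to the AESI reporting guidance in protocol 8.1.2, which leaves the decision to the investigator. SAP 13.4 does not adopt it.
- *The two documents treat values already abnormal at baseline in opposite ways.* SAP 13.4 is silent on them. The protocol's comparison with Baseline may mean no more than showing baseline counts alongside.

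**Conclusion.** The discrepancy is real and should be corrected. Followed as written, the SAP produces a narrower laboratory safety result than protocol 9.4.3 and 9.5 require, and section 14 does not say so. What goes unsummarised is out-of-range results not judged clinically significant, and shifts from baseline, in the laboratory areas the protocol emphasises. Whether falls in blood counts are tabulated is unclear.

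The size is unknown. It is 1 − s, which runs from 25% to 90% over the assumed values above, and the documents do not narrow that range. The efficacy analyses are untouched.

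One assumption applies. SAP 14 refers to protocol version 3.0, while the protocol supplied is version 2.1. Protocol 3.1 says the versions for US and foreign sites are kept very similar or identical, and this conclusion takes the laboratory wording to be the same in both.

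**What to change.** In SAP 13.4:

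1. Add the count from protocol 9.5: patients with abnormal biochemistry, haematology and urine results, presented against Baseline. State how values already abnormal at baseline are handled.
2. Add shift tables from baseline to post-baseline, low/normal/high for haematology and biochemistry and normal/abnormal for urine, classified by local laboratory ranges. These also provide the normal/abnormal tabulation in protocol 9.4.3 and match the SAP's own treatment of vital signs and fundoscopy.
3. Keep Table 13-6 as a supplement, retitled *Clinically significant abnormal laboratory values (high or low)*.

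Counts of liver tests by multiple of the upper limit of normal would be useful, but they are optional because the protocol does not require them. If the sponsor prefers the narrower output, SAP 14 should declare and justify it.

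The cost is a few extra tables and some SAP wording. Laboratory samples are already scheduled at every visit, and Table 13-6 already needs each value classified against a normal range. The drawback is reliance on local ranges, which may differ between laboratories.

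### The SAP's only laboratory summary pools low with high values and omits the comparison with baseline and the normal/abnormal tabulation that the protocol promises

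*SAP*

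**What the plan says.** **Protocol.** Section 1.2 says that safety will be assessed "with particular emphasis on the proportion of patients experiencing elevated Liver Function Tests (LFTs) or changes in blood cell counts". Section 8.1.2 names two groups of adverse events of special interest (AESI): abnormal liver tests or hepatitis, and "Blood count abnormalities (such as agranulocytosis, anaemia, leukocytopenia or thrombocytopenia". For reporting, section 9.4.3 states: "The clinical laboratory variables and vital signs will be summarized descriptively, including a tabulation of normal and abnormal values". Section 9.5 lists as a secondary safety endpoint: "The count of patients who experienced abnormal biochemistry, haematology and/or urine test results will be reported, compared to the Baseline assessments".

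**SAP.** Section 13.4 says that "the clinical out of normal range laboratory variables with clinically significant values will be tabulated as described in Table 13-6", and adds: "Clinical significance of the out of normal range laboratory variables will be as assessed by the investigator". The table's caption is "Table 13-6- Increased laboratory values". It has one row per test (for example "Platelet Count") and columns for clinically significant events, patients, rate and days in treatment. The only other laboratory output is a listing of test name, value and unit by patient and visit.

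**The concern.** The special-interest blood-count risk lies in one direction, downwards. A table with one count per test, no direction and no baseline does not describe that risk. If three patients appear in the platelet row (a hypothetical figure), the reader cannot tell how many had low counts, or how many of the abnormalities were already there before the first dose.

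The baseline matters more here than in a randomised trial. The two natural history surveys collected no laboratory data (SAP 13.4), so each patient's own baseline is the only comparator available.

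The SAP also narrows what is counted. The protocol speaks of abnormal results. Table 13-6 counts only those abnormal results that the investigator called clinically significant, with no numeric criterion. The protocol lets the SAP supersede it (protocol 9.1), and the SAP claims precedence (SAP section 2). The protocol's laboratory summary would therefore not be produced by default.

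**Working it through.** The point involves no power, sample size or event rate, so the check is a count and a comparison of sections.

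**1. Rows of Table 13-6.** Biochemistry 19, haematology 13, urine 5: 19 + 13 + 5 = 37. Rows with a low/high split: 0. Columns or rows giving a baseline value or a change from baseline: 0.

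**2. Direction of the named risk.** Agranulocytosis, anaemia, leukocytopenia and thrombocytopenia are all low-count conditions: 4 of 4. They correspond to the neutrophil, haemoglobin, white cell and platelet rows, each of which is a single undirected row.

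**3. What the protocol promises and what the SAP plans.**

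| Protocol | SAP 13.4 |
|---|---|
| Descriptive summary of laboratory variables (9.4.3) | Not planned |
| Tabulation of normal and abnormal values (9.4.3) | Not planned; only out-of-range values judged clinically significant |
| Count of patients with abnormal results against baseline (9.5) | Patient count, but restricted by judged significance and without baseline |

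**4. How the SAP treats comparable data.** The protocol 9.4.3 sentence covers laboratory variables and vital signs together. For vital signs, SAP 13.5 plans actual values, change from baseline and shift tables. For fundoscopy, SAP 13.7 plans shift tables. Laboratory data have no such output.

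**5. Is the change declared?** SAP section 14 reports no deviations. It cites protocol version 3.0, whereas the protocol supplied is version 2.1. SAP section 2 names both, and protocol 3.1 says the versions are very similar or identical. The mismatch lowers certainty a little but does not remove the point.

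**6. Can other outputs fill the gap?**
- *Adverse event tables (SAP 13.3).* A low count reported as an adverse event appears by preferred term, and the term carries the direction. But protocol 8.1.2 excludes from AESI reporting those expected fluctuations that the investigator considers not clinically relevant. This route therefore depends on investigator judgement, as Table 13-6 does. Table 13-4 has one AESI row, which pools hepatic and blood-count events.
- *Listing (SAP 13.4).* It includes baseline values but specifies no reference range and no high/low flag. Samples go to local laboratories (protocol 6.6.1 and 8.6.3) at approximately 35 centres, so values cannot be reliably classified from the listing alone.

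**7. Analytes.** Protocol 8.6.3 lists 20 biochemistry tests, with creatinine and creatine kinase as separate items. Table 13-6 has 19, with one row labelled Creatine: 20 − 19 = 1 row short.

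**The case against.** A reader might infer from the caption that only increases will be tabulated and that low counts vanish. The documents do not support that. The sentence introducing the table speaks of values outside the normal range without direction, and the rows include haemoglobin, sodium, albumin and urine pH, an odd choice for a table of increases. A mislabelled caption is the likelier explanation. Correcting it still leaves low and high in one count.

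A reader might also infer that the whole report could not tell a fall in platelets or neutrophils from a rise. That too goes beyond the documents. Adverse events are tabulated by preferred term, AESIs must be reported within 24 hours whatever their severity, and every laboratory value is listed.

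Three further objections deserve weight:

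- Investigator judgement has a basis in the protocol: section 8.1.2 leaves the clinical relevance of hepatic changes to the investigator. A table restricted to clinically significant values is therefore legitimate. The difficulty is that it is the only laboratory table.
- The SAP may supersede the protocol, and protocol 9.5 places its count in the analysis made once all patients have completed Month 12, without prescribing a format. So a different display is not in itself an error, and shift tables are one option, not a requirement. What stands is that the promised content is absent and the absence is undeclared.
- The Creatine row is a labelling slip with one row missing. Neither creatinine nor creatine kinase is an AESI test, so this is editorial.

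**Conclusion.** The point holds for the laboratory summary. Followed as written, SAP 13.4 would not deliver the abnormal-result count against baseline or the normal/abnormal tabulation that the protocol promises. It would also pool low with high values in all 37 rows, including the four that correspond to the named blood-count risks. The plan would give a poorer answer on the safety question that the protocol singles out.

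The limits are clear. The loss is within the laboratory summary, not the whole report, and no efficacy result is affected. The conclusion assumes that protocol version 3.0 carries the same sections 9.4.3 and 9.5 as the version supplied, and that no laboratory table is planned outside SAP 13.4. The general formats in SAP sections 9 and 19.2 do not say that they apply to laboratory data. The change should be made, but it is not critical to the trial.

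**What to change.** In SAP 13.4:

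1. Split each haematology row of Table 13-6 into low and high.
2. Add a low/normal/high tabulation against baseline, regardless of judged clinical significance, at least for the AESI tests: ALT, AST, total bilirubin, GGT, haemoglobin, white cells, neutrophils and platelets. Shift tables like those already planned for vital signs would do this and would satisfy protocol 9.4.3 and 9.5 on normal/abnormal values and baseline.
3. As editorial corrections, retitle the table 'Out-of-range laboratory values' so that it agrees with its text, and replace the Creatine row with separate creatinine and creatine kinase rows.

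If the sponsor prefers to keep 13.4 as it stands, section 14 should declare the departure from the protocol.

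The cost is small. Table 13-6 grows from 37 to 37 + 13 + 1 = 51 rows, and the baseline tabulation covers eight tests. Blood is already taken at every visit, including baseline, so no new data are needed. Classifying values as low or high requires the local laboratories' reference ranges, which the out-of-range rule in SAP 13.4 already presupposes.
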